3 STUDY OBJECTIVE(S) AND DESIGN

3.1 Study Objective(s)

3.1.1 Primary Objective

The primary objective is to compare the incidence of a two-part composite endpoint consisting of de novo donor specific antibody (DSA) formation or a designation of immune activation (IA) on peripheral blood molecular profiling in subjects maintained on twice daily, immediate-release tacrolimus versus those maintained on Astagraf XL in the first year post-transplant.

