4 SAMPLE SIZE

The sample size for this study was determined based upon a comparison of the rate of the two-part composite endpoint in the Astagraf XL group compared to the immediate-release tacrolimus group. Assuming a rate of 20% would be observed for the immediate-release tacrolimus group compared to a rate of 10% for the Astagraf XL group, 220 subjects per group are needed to achieve an 80% power to detect a difference between Astagraf XL and immediate-release tacrolimus with a two-sided alpha level of 0.05. The study will enroll 275 subjects/group (550 total) to allow for 20% dropout.

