7.4.1 Analysis of Primary Endpoint(s)

7.4.1.1 Primary Analysis of Primary Endpoint

The primary analysis will be performed on the primary composite endpoint of combined incidence of either De Novo DSA or IA on molecular blood profiling at one year. Both De novo DSA (Positive/Negative) and IA (Present/Absent) will be considered binary. DSA positivity is assessed by the Transplant Immunology Lab of Northwestern University.

In the case where MFI signal is greater than 1000, and DSA is suspected, but the formation of De Novo DSA cannot be confirmed due to inadequate donor typing, the formation of De Novo DSA will be labeled indeterminate. If subject discontinues the study between D0 and D30, and no testing results are available, then De Novo DSA will be assumed to be negative. If subject does not have a specimen collection, then De Novo DSA will be assumed missing and will be excluded from primary efficacy analysis, but will be assumed to be negative in

sensitivity analysis. The table below shows the logic set up for actual assessment of study composite endpoint.

De Novo DSA	IA	Study Composite Endpoint
Positive	Present	Positive
Positive	Not Present	Positive
Positive	Unknown	Positive
Negative	Present	Positive
Negative	Not Present	Negative
Negative	Unknown	Indeterminate
Indeterminate	Present	Positive
Indeterminate	Not Present	Indeterminate
Indeterminate	Unknown	Indeterminate

The proportion of subjects meeting the primary composite endpoint definition will be summarized by treatment group. The difference in the proportion of subjects meeting the primary composite endpoint definition and 95% confidence interval will also be provided.

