The primary analysis of the treatment group comparison will be based on fitting a multivariable binary logistic regression model with randomized treatment group (Astagraf XL group versus twice-daily, immediate-release tacrolimus group), pre-defined randomization stratification factors (planned use of Campath [Yes/No], levels of KDPI as defined in Section 4.5 of the protocol, and HLA Class II mismatch), recipient age, gender, and race, and pre-transplant cPRA included in the model. Investigational site will be included as a random effect. The limited numbers of subjects per center, however, may make it impracticable to include all sites in the statistical model. If reasonable, data from low enrolling sites (e.g., < 5 subjects) will be combined. The decision to include sites and how to combine sites, if necessary, will be made prior to database unblinding.

Adjusted (common) odds ratio (OR: Astagraf XL group versus immediate-release tacrolimus group) and two-sided exact 95% CI will be provided as measures of strength of association and precision, respectively. The null hypothesis of no treatment effect can be expressed as $H_0: OR = 1$ and will be tested at the ≤ 0.05 level using the Wald's chi-square statistic on one degree of freedom. Odds ratio will also be estimated for the covariates included in the model.

Subjects with primary endpoint unknown, undetermined, or missing will be excluded from the primary analysis.

The hypothesis for the comparison is as follows:

H₀: The proportion of subjects with the primary endpoint is the same between subjects receiving Astagraf XL and subjects receiving immediate-release tacrolimus.

H₁: The proportion of subjects with the primary endpoint is not the same between subjects receiving Astagraf XL and those receiving immediate-release tacrolimus.

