7.10 Handling of Missing Data, Outliers, Visit Windows, and Other Information

7.10.1 Missing Data

Generally, all missing efficacy endpoints (e.g. DSA, IA, pathological findings, eGFR) will not be imputed. Only for the sensitivity analyses, e.g. the sensitivity analysis of primary endpoint (section 7.4.1.2), the indetermined endpoint will be imputed as Negative.

In AE summary tables, the missing AE severity and relationship to study drug will be replaced with the highest level of severity and relationship: “Severe” and “Probable”, respectively. In AE data listing, original missing data will be displayed.

As a general principle, no imputation of missing data for other variables will be done.

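### The composite-endpoint table keeps half-observed subjects only when they are events, which inflates the reported event rates and risk difference, though not by itself the odds ratio

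*SAP*

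**What the plan says.** The primary objective (SAP 3.1.1) is to "compare the incidence of a two-part composite endpoint" between the randomised groups over the first year. SAP 7.4.1.1 derives that composite from a nine-row grid: "The table below shows the logic set up for actual assessment of study composite endpoint". Four rows have exactly one unresolved component:

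| DSA | IA | Composite | Primary analysis |
|---|---|---|---|
| Positive | Unknown | Positive | kept, as an event |
| Negative | Unknown | Indeterminate | dropped |
| Indeterminate | Present | Positive | kept, as an event |
| Indeterminate | Not Present | Indeterminate | dropped |

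The dropping comes from the same section: "Subjects with primary endpoint unknown, undetermined, or missing will be excluded from the primary analysis".

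Four related provisions matter:

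- **DSA Indeterminate** means tested but unresolved: MFI above 1000 and DSA suspected, but donor typing too poor to confirm it.
- **No DSA specimen:** the text treats DSA as missing and removes the subject from the primary analysis. The grid has no row for this case.
- **Leaving between Day 0 and Day 30 without results:** "then De Novo DSA will be assumed to be negative".
- **Sensitivity analysis** (SAP 7.4.1.2 and 7.10.1): "the indetermined endpoint will be imputed as Negative". The FAS and PPS analyses reuse the primary logistic model.

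SAP 7.4.1.1 reports the proportion per arm and the risk difference with a 95% interval. The hypothesis test is a Wald test of the covariate-adjusted odds ratio.

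**The concern.** Scoring a subject as positive when either component is positive is logically correct. The difficulty is pairing that rule with removal of the matching negatives. Within the four rows above, a subject can enter the primary analysis only as an event. What is estimated is then the incidence among fully determined subjects plus the positive part of the half-observed ones, not the incidence in the randomised groups. This happens even if results are lost purely by chance.

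The negative-imputation analysis does not repair it. It scores as non-events some subjects whose unknown component would have been positive, so it errs the other way.

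The Day 0-30 sentence also has no effect on the composite. Such a subject has DSA set to negative but IA unknown, falls in the Negative/Unknown row, and is dropped.

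**Working it through.** **The plan's own figure.** SAP section 4: "Assuming a rate of 20% would be observed for the immediate-release tacrolimus group compared to a rate of 10% for the Astagraf XL group", with "220 subjects per group are needed to achieve an 80% power" at a "two-sided alpha level of 0.05". The continuity-corrected two-proportion formula gives 219 per group, and Fisher's exact test at 220 per group has power 0.811, so 220 reproduces. 220 / 0.80 = 275. The planned odds ratio is (0.10/0.90) / (0.20/0.80) = 0.444.

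**Inputs.** From the SAP: true composite rates p = 0.20 and 0.10. Not in the documents, so assumed: u, the share with exactly one component unresolved, at 5%, 10% and 20%; and s, the fraction of composite events that the known component captures alone, at 50% and 75%. Then d = s·p is the rate of the known component. Missingness is completely random.

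**Formulas.**

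- SAP primary rule: rate = [(1−u)p + u·d] / [(1−u) + u·d].
- Its bias: u·d·(1−p) / (1−u+u·d), which is above zero whenever u and d are above zero and p is below 1.
- Negative imputation: rate = (1−u)p + u·d.

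Example for control, u = 0.10, s = 50%, d = 0.10: (0.18 + 0.01) / (0.90 + 0.01) = 0.2088. Negative imputation gives 0.18 + 0.01 = 0.19.

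| u | s | Control, SAP rule | Astagraf XL, SAP rule | Difference (points) | Control, negative imputation | Difference, negative imputation (points) |
|---|---|---|---|---|---|---|
| 5% | 50% | 20.42% | 10.24% | 10.18 | 19.50% | 9.75 |
| 5% | 75% | 20.63% | 10.35% | 10.27 | 19.75% | 9.88 |
| 10% | 50% | 20.88% | 10.50% | 10.38 | 19.00% | 9.50 |
| 10% | 75% | 21.31% | 10.74% | 10.57 | 19.50% | 9.75 |
| 20% | 50% | 21.95% | 11.11% | 10.84 | 18.00% | 9.00 |
| 20% | 75% | 22.89% | 11.66% | 11.24 | 19.00% | 9.50 |

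**Simulation check.** Composite rate 20%, DSA rate 11%, IA unknown in 10% at random. The SAP rule gives 0.210; restriction to subjects with both components determined gives 0.200.

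**Odds ratio.** Retained events are p[(1−u) + u·s] and retained non-events are (1−u)(1−p). The retained odds are therefore the true odds times [(1−u) + u·s] / (1−u). If u and s are the same in both arms, this factor cancels and the unadjusted odds ratio is 0.444 in every row above. It does not cancel if they differ:

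- No true effect (20% in both arms), s = 50%, u = 15% in Astagraf XL and 5% in control: 21.39% against 20.42%, odds ratio 1.06.
- True 20% against 10%, u = 20% in both arms, s = 25% in Astagraf XL and 75% in control: odds ratio 0.398. With the shares reversed: 0.497.

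**No DSA specimen.** With 10% of DSA specimens missing at random and those subjects excluded as the text says, the simulated rate is 0.200, so there is no inflation. Had the IA-positive ones been kept, it would be 0.209.

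**The case against.** The strongest reply is that the primary test concerns the odds ratio, and under random missingness that is equal across arms the unadjusted odds ratio is untouched. This stands. A reader might infer that the rule biases the trial's main comparison or inflates its type I error. That requires the half-observed share or the component mix to differ by arm, and the documents quantify neither. A split of 5% against 20% half-observed (about 14 against 55 of 275) with no true effect would give a type I error of 7.0-9.3%, but nothing in the documents supports such a split. The 20% dropout allowance is no anchor for it either. DSA and molecular samples are scheduled at the same visits (Schedule of Assessments) and phlebotomy sessions (Protocol 5.8), so dropout tends to remove both results rather than one.

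A reader might also infer that any subject missing either assay can enter only as an event. The documents do not support that. A subject with no DSA specimen is excluded whatever the IA result, and with up to five joint samples in year one, having no IA result at all should be uncommon. Indeterminate DSA is unlikely to be random, and Protocol 5.7.3 expects extra donor typing to be needed only rarely and gives a route to obtain it. The formula above fits IA Unknown; it is not a guide to the size of the effect for Indeterminate DSA.

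Finally, the primary and negative-imputation analyses bracket the true rate under random missingness. That is correct, but neither estimates it. The open allowance in SAP 7.4.1.2 for further sensitivity analyses commits to nothing.

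**Conclusion.** The point holds for the reported rates and the risk difference. The grid and the exclusion sentence together make inclusion depend on outcome, and the direction of the bias under random missingness follows algebraically. Its size is modest and rests on assumed inputs: over 5-20% half-observed and 50-75% of events captured by the known component, control moves from 20% to 20.4-22.9% and the difference from 10 points to 10.2-11.2. At the low end it is close to negligible.

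No distortion of the odds ratio or the type I error is shown. In an open-label trial, unequal missingness between arms is possible, but only counts by arm would tell. The cancellation was shown for the unadjusted odds ratio; the planned one is covariate-adjusted and was not computed separately. The change is worth making because the primary endpoint is affected and no committed analysis gives unbiased rates under random missingness.

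**What to change.** Keep the rule that either positive component makes the composite positive, and amend SAP 7.4.1.1 and 7.4.1.2 before database lock:

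1. Pre-specify an analysis restricted to subjects with both components determined, so that positives and negatives face the same evaluability rule. Under random missingness this returns 20.0% and 10.0%.
2. Optionally, add multiple imputation of the unknown component, deriving the composite in each imputed data set and fitting the planned logistic model. For Indeterminate DSA the imputation model should include MFI, because a signal above 1000 is what defines those subjects; leaving it out would probably impute too few positives. This adds a missing-at-random assumption.
3. State how a subject with no DSA specimen but a known IA result is handled, and add the rows to the grid. Define when a subject's IA is Unknown.
4. Reconcile the Day 0-30 negative rule with the Negative/Unknown row for the composite. Keep the rule for de novo DSA, which is a secondary endpoint in its own right.
5. Report the number of subjects in each grid row by arm. These counts alone would show whether the bias is trivial and whether it differs between arms.

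The cost is SAP wording and modest programming, with no new data or patients. The rates from the added analysis would be slightly lower than under the present grid.

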7.4.1.2 Sensitivity Analyses of Primary Endpoint

A sensitivity analysis, based on missing data imputation, will be included for the mFAS. Subjects that have missing or incomplete data who did not permanently switch therapy or were discontinued from the study prior to a DSA/IA event, who are lost to follow up, or those who expire for any reason, negative DSA/IA values will be imputed.

A sensitivity analysis using the FAS will be conducted on the primary endpoint. The logistic regression analysis described in Section 7.4.1.1 will be used.

A secondary analysis using the PPS will be conducted on the primary endpoint data. The logistic regression analysis described in Section 7.4.1.1 will be used.

Additional sensitivity analysis under different assumptions may be conducted in the future to address specific research questions.

7.4.2 Analysis of Secondary Endpoints

Risk factor analysis will be conducted in two parts. First, is to identify risk factors for outcomes based on factors measured at time of transplantation (baseline) including the pre-defined stratification factors. Last, is to identify risk factors for outcomes based on factors that are measured post-randomization and therefore, are subject to change e.g., average daily dose of MPA treatment or cumulative dose of corticosteroids. All models will include randomized treatment, irrespective of statistical significance. Models to assess risk factors for binary or categorical variables will be done using logistic regression. Odds ratio and 95% CI will be used as measures of strength of association and precision, respectively.

Risk factor analyses will be conducted for eight binary variables: IFTA, IFTA and Inflammation, BPAR, the four-part traditional composite endpoint, early MMF interruption/discontinuation, and eGFR status based on three thresholds 30, 40, and 50. The biopsy data are based on the central pathology results over the course of one year plus 2 months window. eGFR status variables are based on the assessment at Day 365 visit.

Each risk factor analysis model will include treatment group and a main factor: either De novo DSA, IA, or the composite of De novo DSA and IA. Following additional covariates will be considered for the two types of models, and a multicollinearity assessment will be proceeded for the final variable selection:

Risk factors measured at time of transplantation include:

- Cold ischemic time
- Warm ischemic time

- KDPI% \leq 50% (yes/no)
- KDPI% $>$ 50% (yes/no)
- HLA Class II mismatch (yes/no)
- Donor status (living/deceased)
- Donation after circulatory death (yes/no)
- Donor Age
- Donor-Recipient sex mismatch (match/mismatch)
- Donor-Recipient race mismatch (match/mismatch)
- Preservation by cold storage (yes/no)

Post randomization risk factors include:

- Cumulative Dose of Corticosteroids
- Average daily dose of MPA
- Mean dose level of tacrolimus
- Mean tacrolimus trough level
- Number of excursions below 80% or above 120% of the average tacrolimus trough level
- IPV estimated by CV%
- Post-transplant BK virus infection

Following secondary endpoints will be summarized with frequencies and percentages by treatment group. The incidence of events will be analyzed for treatment group differences. Analysis of treatment group differences will be implemented from logistic regression model with the same covariates of primary efficacy analysis.

1. De novo DSA formation
2. IA
3. C1q-binding DSA
4. DSA IgG₃ isotype
5. Persistence of DSA
6. Persistence of IA
7. TG (cg $>$ 0)
8. Microcirculatory Inflammation (g+ptc $>$ 2)

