6 DISCONTINUATION

6.1 Discontinuation of Individual Subject(s)

A discontinuation is a subject who enrolled in the study and for whom study treatment is permanently discontinued prematurely for any reason.

The subject is free to withdraw from the study treatment and/or study for any reason and at any time without giving reason for doing so and without penalty or prejudice. The investigator is also free to terminate a subject's involvement in the study at any time if the subject's clinical condition warrants it.

If a subject is discontinued from the study with an ongoing AE or an unresolved laboratory result that is significantly outside of the reference range, the investigator will attempt to provide follow-up until the condition stabilizes or no longer is clinically significant. However, other than pertinent information regarding the AE (i.e., follow-up laboratory values, AE information updates, etc.), no additional clinical information will be collected following the discontinuation.

Discontinuation Criteria from Study for Individual Subjects:

- Subject develops allograft loss (as defined by subject death, retransplantation, transplant nephrectomy, or return to dialysis of ≥ 6 consecutive weeks duration);
- Subject develops unacceptable toxicity or is withdrawn at the discretion of the patient's supervising physician;
- Subject is lost to follow-up despite reasonable efforts by the investigator to locate the subject;
- Subject withdraws consent for further treatment or expires during the course of the study;
- Subject begins taking any prohibited medications (see Section 5.1.5);
- Subject undergoes a second organ transplant;
- Conversion to a non-tacrolimus-based maintenance regimen in either study arm if required to manage toxicities;
- Removal from an MMF-containing immunosuppressive regimen (or its equivalent);
- Failure to achieve a tacrolimus whole blood concentration ≥ 6 ng/mL for 4 consecutive weeks during the first 6 weeks following transplantation;
- Permanent withdrawal of tacrolimus;
- Interruption or prolonged significant reduction of tacrolimus (as an example, a 50% reduction or dose at a level of less than 3.5ng/mL) for periods exceeding 4 weeks;

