Follow-up visits will be performed quarterly during the first year of follow-up to collect standard clinical data. For follow-up beyond the first year, urinary protein, and tacrolimus trough concentrations obtained closest to targeted date of visit, per SoC, should be recorded. Up to two serum creatinine levels obtained at least one month apart, if performed per SoC, should also be recorded. Additionally, all local kidney biopsy results, AEs, and concomitant medications pertaining to AEs will be recorded. If the study progresses to two years, at the terminal study visit at 24 months, the most recently obtained lab results as well as any episodes of rejection, need for antibody reduction, graft loss, and deaths occurring beyond the first year will be detailed in the electronic Case Report Form (eCRF). Final testing for DSA and molecular profiling will also be performed at the 24 month visit.

Pathology results [hematoxylin and eosin (H&E), light microscopy, and immunofluorescence] will be appended to the eCRF when local kidney biopsies are performed and interpreted during the course of clinical care. De-identified copies of all kidney pathology reports must be submitted to Astellas. For all participants who undergo at least one kidney biopsy during the first year post-transplant (either for cause or per institutional protocol), the kidney biopsy performed closest to the 12 month visit (but no later than 14 months post-transplant) will be submitted for central pathological grading. All biopsies that are submitted for central pathology review will be evaluated and scored using the most recent version of the 2007 Update to the Banff '97 Classification by a central pathologist blinded to clinical results and subject identifiers.

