These threshold endpoints will be calculated for months 1, 3, 6, 9, and 12 using the Modification of Diet in Renal Disease (four variable-MDRD) criteria. Assessments are positive or negative.

- Five-point decline in eGFR

The decline in eGFR will be calculated with respect to the eGFR value at Day 30 visit.

- Traditional transplantation composite endpoint

Incidence will be assessed at month 12 for the following:

- Graft loss (defined as retransplantation, transplant nephrectomy, or a return to dialysis for at least a six week duration, or subject death)
- Death
- BPAR – positivity will be determined by local biopsy, central pathology, or reported adverse events.
- Composite occurrence of either graft loss, death, BPAR, and loss-to-follow-up

- Histopathology grading within 1 year

Central histopathology grading over 1 year will be diagnosed according to the BANFF diagnostic categories and subcategories that include the following:

- Normal
- Antibody mediated changes
 - C4d deposition without morphologic evidence of active rejection
 - Acute ABMR (grades: I, II, and III)
 - Chronic active ABMR
 - ABMR: either Acute ABMR or Chronic Active ABMR
- Borderline changes
- TCMR
 - Acute TCMR (grades: IA, IB, IIA, IIB, and III)
 - Chronic active TCMR
- IFTA (grades: I, II, and III)
- Other: all categorical findings will be summarized.
- In addition to the categories above, specimens will be given individual scores for the following: glomerulitis (g), tubulitis (t), intimal arteritis (v), mononuclear cell interstitial inflammation (i), early allograft Glomerulopathy (cg), tubular atrophy (ct), interstitial fibrosis (ci), vascular fibrous intimal thickening (cv), arteriolar hyaline thickening (ah), peritubular capillaries (ptc) and mesangial matrix (mm).

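### The post-randomization risk-factor models use exposure windows that do not end before the outcome, and they enter trough excursions as a raw count, so sampling frequency, early leaving and rejection treatment can appear as risk or protective factors

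*SAP*

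**What the plan says.** SAP 7.4.2 plans risk-factor models for eight binary outcomes: IFTA, IFTA with inflammation, BPAR, the four-part composite, early MMF interruption or discontinuation, and eGFR below 30, 40 and 50. A first part uses factors known at transplantation. The second is described as follows: "Last, is to identify risk factors for outcomes based on factors that are measured post-randomization and therefore, are subject to change". Its covariates include "cumulative dose of corticosteroids", "average daily dose of MPA", mean tacrolimus dose and trough, CV%, BK infection, and "Number of excursions below 80% or above 120% of the average tacrolimus trough level". The method is logistic regression with odds ratios and 95% CIs.

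SAP 7.3.3 observes that troughs are not tied to scheduled visits and that subjects may differ in how many they have. Its item 2 defines excursions as a proportion of troughs. The same section then names the number of excursions as the model covariate.

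SAP 7.10.3 takes study treatment and troughs from Day 30 to Day 365 (after Day 42 for variability) and cuts total immunosuppressant dose at Day 365. Central pathology counts from Day 0 to Day 426.

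For BPAR, SAP 6.1.2 says "positivity will be determined by local biopsy, central pathology, or reported adverse events". SAP 7.4.2 says "The biopsy data are based on the central pathology results over the course of one year plus 2 months window". SAP 3.2 says which biopsy is read centrally: for anyone biopsied in year 1, "the kidney biopsy performed closest to the 12 month visit (but no later than 14 months post-transplant) will be submitted for central pathological grading".

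Protocol 6.1 lists death, graft loss and loss to follow-up as reasons for discontinuation. Apart from information on adverse events, "no additional clinical information will be collected following the discontinuation". Rejection itself is not on the list.

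**The concern.** A risk factor has to act before the outcome. Here nothing requires the exposure to come first. A subject with rejection at Month 3 stays in the study, and the exposure record runs on to Day 365, including whatever was given or measured because of the rejection. For an event before Day 30, the whole trough window lies after the outcome.

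A subject who dies, loses the graft or is lost to follow-up has a shortened record, and each of these is a component of the composite. Protocol 7.4.2 defines loss to follow-up by failure to complete the final visit without prior BPAR, graft loss or death. Most early leavers are therefore composite events by definition, and their totals are short for the same reason.

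The excursion count adds a third route: it rises with the number of troughs drawn, however stable the subject is.

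Risk factors are the first-listed secondary objective, and SAP 7.1 does not adjust p-values. A consequence of rejection, or of leaving, could be published as a cause of it or as protection from it.

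**Working it through.** **The plan's own threshold.** SAP 7.1 runs no regression when the event rate is below 10%, given as fewer than 57 subjects. 57 / 0.10 = 570 subjects, used below. (Ten per cent of the planned 550 would be 55.)

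**1. Count against proportion, by formula.** Protocol 1.2.5 gives a trough CV of about 15% in stable patients. Assuming normal troughs, P(outside 80% to 120% of own mean) = 2 × [1 − Φ(0.20/0.15)] = 0.182. Expected count = 0.182 × number of troughs:

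| Troughs | 6 | 12 | 24 | 36 |
|---|---|---|---|---|
| Expected excursions | 1.1 | 2.2 | 4.4 | 6.6 |

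The count rises sixfold with no change in variability; the expected proportion stays at 0.182.

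**2. Count against proportion, by null simulation.** The documents do not give sampling frequency by outcome, so it is assumed.

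- *Extra troughs only after rejection.* 440 subjects, 15% with events, event date uniform over the year, mean 12 troughs with the rate varying by subject, CV about 15%. With troughs 1, 1.5, 2 and 3 times as frequent after the event, the count is significant at 0.05 in 4%, 53%, 94% and 100% of runs (median OR per SD 1.01, 1.28, 1.53, 2.05). The proportion is significant in 4% to 6%.
- *More troughs in cases over the whole year.* 570 subjects, BPAR 12%, CV 15% to 35%, cases with 1.25 to 1.5 times the troughs. If troughs follow a Poisson distribution with one common rate, the count OR is 1.56 to 4.78. If the rate varies by subject (overdispersed), it is 1.33 to 1.92, with 61% to 100% of runs significant. The proportion gives 0.99 to 1.06 (0% to 6%).

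**3. Rejection steroids.** Assume a maintenance total with mean 2000 mg and SD 800 or 1500 mg, and 250 to 1500 mg added after the event in 50% to 75% of cases. The OR per SD for cumulative dose is 1.08 to 3.25 (10% to 100% of runs significant). With the added courses excluded it is 0.99 to 1.01 (3% to 7%).

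**4. Early leaving, four-part composite.** Two sets of assumptions:

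| | Cumulative steroid OR | Excursion count OR |
|---|---|---|
| Constant daily dose; 5%, 10%, 20% lost; 15% other events | 0.65, 0.50, 0.36 | 0.83, 0.74, 0.63 |
| Half the dose in first 30 days; composite 18%; 25% to 50% of event subjects leave early | 0.91 to 0.68 | 0.72 to 0.50 |

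Higher exposure looks protective in both. In the first set, dose per day of follow-up is significant in 4% to 8% of runs and the excursion proportion in 7% to 9%.

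**5. Truncating cases is not a remedy.** Cutting cumulative steroid dose at the event in cases only gives 0.39 to 0.62 (86% to 100% significant), because cases then accumulate for a shorter time.

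**6. What the proportion leaves behind.** With equal sampling, CV 20% and a 20% shift in trough level after the event, the proportion still gives 1.33 to 1.57, CV% 1.40 to 1.67, and mean trough 1.76 or 0.48, depending on the direction of the shift. A 10% shift gives 1.09 to 1.12, 1.11, and 1.37 or 0.71.

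**7. Will the models run?** The exact binomial chance of fewer than 57 BPAR events in 570 is 95% at a rate of 8%, 48% at 10% and 6% at 12%. For a landmark analysis, with events uniform over Day 7 to 365, the chance of at least 57 after Day 90 is 28% at 12% and 89% at 15%. After Day 180 it is 0% at 12% and 62% at 20%.

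**The case against.** **The trial is exploratory, the SAP separates baseline from post-randomization factors, and it calls the odds ratio a measure of association.** True, and it limits the severity. But the stated purpose is still to identify risk factors, and nothing tells the reader that time order is not established. The multicollinearity check does not address time order.

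**The count may be only a label, since SAP 7.3.3 item 2 derives a proportion.** Possible. But both covariate lists say number, and the literal reading is a count. If a proportion was meant, the correction is a change of wording.

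**The sizes rest on assumed inputs.** They do. The larger odds ratios need a common sampling rate across subjects; standard-of-care sampling at some 25 to 30 centers makes variation more plausible. The direction survives that change; an odds ratio near 4.8 does not.

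**The corticosteroid window is inferred.** Correct. The SAP does not define cumulative corticosteroid dose. The Day 365 cut is read from the entry for total immunosuppressant dose.

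**If BPAR is read centrally, the biopsy is near Month 12 and little exposure follows it.** A reader might infer this, but the documents do not support it. The biopsy submitted is the one closest to Month 12, so a subject whose only biopsy was an early one for cause is read on that biopsy, and central pathology counts from Day 0. By the same reasoning the IFTA outcomes are not exempt merely because they are centrally read. What does stand is that the analysis would then move to the biopsy set (SAP 7.4), and the event probabilities for 570 subjects would not apply.

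**Conclusion.** The concern holds in a bounded form. The windows are calendar windows that do not end before the outcome. The excursion covariate is a raw number where a proportion is already defined. For BPAR and the composite, cumulative steroid dose can contain treatment for the event, and it and the excursion count are cut short by leaving. The text establishes the mechanism and, for sampling frequency and truncation, the direction. The sizes are illustrative: for the count, an OR per SD of about 1.3 to 1.9 at 1.25 to 1.5 times the troughs with overdispersed sampling.

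Four stronger readings do not follow:

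- *The SAP sets no exposure window.* It does; the windows are simply not tied to the outcome.
- *All eight models and all the covariates are biased alike.* Shortened accumulation affects only the cumulative corticosteroid dose and the excursion count. Per-day and per-measurement covariates do not accumulate in this way, and for eGFR read at Day 365 the exposure mostly comes first.
- *The differing BPAR sources in SAP 6.1.2 and 7.4.2 are a further fault of the same kind.* They need clarification, because the event date depends on them, but the difference does not itself create bias.
- *The trial's main result is in doubt.* The primary analysis uses none of these covariates.

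The BPAR model may never run under the 57-event rule; the documents give no BPAR rate. A correction before analysis is worthwhile but not critical.

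**What to change.** In SAP 7.4.2 and 7.3.3:

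1. Replace the number of excursions with the proportion in 7.3.3 item 2, using each subject's own troughs as denominator. This removes most of the sampling artefact, but not the effect of trough changes after the event.
2. Exclude steroids given to treat rejection from cumulative corticosteroid dose, where records allow. This does not remove other steroid increases after rejection, or short accumulation in early leavers.
3. Do not use average daily MPA dose to predict early MMF interruption. SAP 6.5 defines an average daily dose for study drug only, so the denominator is open; over calendar days, the interruption itself would lower the average.
4. State which BPAR source and event date these models use.
5. Report the remaining post-randomization odds ratios for event-type outcomes as associations without established time order. Add a landmark analysis, with exposure over a common window in subjects event-free at its end, only where the 57-event rule permits. Do not cut exposure at the event in cases only.

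**Cost:** SAP wording and small derivation changes. Items 1, 3, 4 and 5 need no new data. For item 2, anti-rejection therapy is recorded (footnote 7 to the schedule of assessments), but the documents do not say whether each steroid record carries an indication.
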